7.2.3 Management of Adverse Reactions from Cabozantinib

Withhold CABOZANTINIB for NCI CTCAE Grade 4 adverse reactions, and for Grade 3 or intolerable Grade 2 adverse reactions that cannot be managed with a dose reduction or supportive care.

Upon resolution/improvement (i.e., return to baseline or resolution to Grade 1) of an adverse reaction, reduce the dose as follows:

- If previously receiving 60 mg daily dose, resume treatment at 40 mg daily
- If previously receiving 40 mg daily dose, resume treatment at 20 mg daily
- If previously receiving 20 mg daily dose, resume at 20 mg if tolerated, otherwise, discontinue CABOZANTINIB

Permanently discontinue CABOZANTINIB for any of the following:

- development of unmanageable fistula or GI perforation
- severe hemorrhage
- arterial thromboembolic event (e.g., myocardial infarction, cerebral infarction)
- hypertensive crisis or severe hypertension despite optimal medical management
- nephrotic syndrome
- reversible posterior leukoencephalopathy syndrome

In Patients Concurrently Taking a Strong CYP3A4 Inhibitor: Reduce the daily CABOZANTINIB dose by 20 mg (for example, from 40 mg to 20 mg daily). Resume the dose that was used prior to initiating the CYP3A4 inhibitor 2 to 3 days after discontinuation of the strong inhibitor

In Patients Concurrently Taking a Strong CYP3A4 Inducer: Increase the daily CABOZANTINIB dose by 20 mg (for example, from 40 mg to 60 mg daily or from 20 mg to 40 mg daily) as tolerated. Resume the dose that was used prior to initiating the CYP3A4 inducer 2 to 3 days after discontinuation of the strong inducer. The daily dose of CABOZANTINIB should not exceed 80 mg.

In Patients with Hepatic Impairment: Reduce the starting dose of CABOZANTINIB to 20 mg once daily in patients with mild or moderate hepatic impairment. CABOZANTINIB is not recommended for use in patients with severe hepatic impairment.

Nursing Guidelines

Monitor vital signs prior to infusion, then every 15 minutes until 1 hour after infusion on first dose.

All patients with a history of infusion reactions to this immunotherapy should be monitored every 15 minutes until 1 hour after the end of the infusion.

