7.2.2 Adverse Events from Cabozantinib monotherapy

Consult the package insert and investigator brochure for the most current and complete information.

The **most frequent AEs experienced** by $\geq 20\%$ of subjects treated with Cabozantinib in descending order of frequency were diarrhea, fatigue, nausea, decreased appetite, vomiting, weight decreased, PPE, constipation, hypertension, dysgeusia, dysphonia, and asthenia. For a full description of the safety profile of Cabozantinib, refer to the Cabozantinib Investigator's Brochure.

Other **medically important** but less frequent AEs including arterial thrombotic AEs (e.g., TIA, and MI) and venous thrombotic AEs (e.g., DVT and PE), severe hemorrhagic events, proteinuria, wound-healing complications, GI perforation, abscesses including intra-abdominal and pelvic abscess, GI and non-GI fistula formation, osteonecrosis, and Reversible Posterior Leukoencephalopathy Syndrome (RPLS).

Adverse events associated with **laboratory abnormalities** experienced by $\geq 5\%$ of subjects treated with Cabozantinib in descending order of frequency were anemia, AST increased, ALT increased,

hypothyroidism, hypokalemia, hypomagnesemia, thrombocytopenia, hypocalcemia, hypophosphatemia, lactate dehydrogenase (LDH) increased, lipase increased, neutropenia, hyponatremia, ALP increased, leukopenia, and hyperglycemia.

Adverse events may occur within the first few weeks in the course of treatment with Cabozantinib, as Cabozantinib is expected to reach steady state exposure at approximately 2 weeks following first dose. Events that generally have an **early onset** include hypocalcemia, hypokalemia, thrombocytopenia, hypertension, PPE, abdominal pain, mucosal inflammation, constipation, diarrhea, and vomiting. Adverse events should be managed with supportive care at the earliest signs of toxicity. Dose reductions and treatment interruptions should be considered. Dose reductions are recommended for events that, if persistent, could become serious or intolerable.

Cabozantinib should be discontinued for the following AEs:

visceral perforation or fistula formation, severe hemorrhage, serious arterial thromboembolic events, nephrotic syndrome, hypertensive emergency, persistent uncontrolled hypertension despite optimal medical management, and RPLS.

Gastrointestinal Disorders

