- b. Therapeutic doses of LMWH or anticoagulation with direct factor Xa inhibitors rivaroxaban, edoxaban, or apixaban in subjects without known brain metastases who are on a stable dose of the anticoagulant for at least 1 week before first dose of study treatment without clinically significant hemorrhagic complications from the anticoagulation regimen or the tumor.

Arterial thrombotic events (e.g., TIA, MI) have been observed in studies with Cabozantinib. Further treatment with Cabozantinib should be discontinued in subjects who develop an acute MI, cerebral infarction, or any other clinically significant arterial thromboembolic complication.

Hypertension

Appendix D provides treatment guidelines for hypertension deemed related to Cabozantinib. Blood pressure should be monitored in a constant position visit to visit, either sitting or supine in

a relaxed setting. Decisions to reduce or interrupt the dose of study treatment must be based on BP readings taken by a medical professional and must be confirmed with a second measurement at least 5 minutes following the first measurement. Cabozantinib should be discontinued in subjects with hypertensive emergency.

Stomatitis and Mucositis

Preventive measures may include a comprehensive oral examination to identify and treat any potential risk for complications before study treatment is initiated. Appropriate correction of local factors should be instituted as indicated, such as modification of ill-fitting dentures and appropriate care of gingivitis. During treatment with Cabozantinib, good oral hygiene and standard local treatments such as non-traumatic and non-irritating cleansing, and oral rinses (e.g., with a weak solution of salt and baking soda) should be maintained. Lips should be kept moisturized with lip balm. The use of lipstick, lip-gloss, and Vaseline should be avoided.

Local treatment should be instituted at the earliest onset of symptoms. Obtain bacterial/viral culture if oral infection is suspected and treat infection as clinically indicated.

Skin and Subcutaneous Tissue Disorders

Wound healing and surgery:

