Tolerable Grade 1-2 (duration < 48 h)	
 • Continue with study treatment and consider GI recommendations • Initiate treatment with an antidiarrheal agent (e.g., loperamide 4 mg followed by 2 mg after each episode of diarrhea [maximum: 16 mg loperamide per day]) • Dietary modifications (e.g., small lactose-free meals, bananas and rice) • Intake of isotonic fluids (1-1.5 L/day) • Re-assess after 24 hours: 
 ○ Diarrhea resolving to baseline bowel habits: gradually add solid foods and discontinue or decrease antidiarrheal treatment after 12 h diarrhea-free interval ○ Diarrhea not resolving: Continue/resume antidiarrheal treatment
Intolerable Grade 2, Grade 2 > 48 h, or \geq Grade 3	
 • Interrupt study treatment • Ask subject to attend clinic • Rule out infection (e.g., stool sample for culture) 
 ○ Administer antibiotics as needed (e.g., if fever or Grade 3-4 neutropenia persists > 24 h) • Administer fluids (1-1.5 L/day orally or IV, as appropriate) for hydration or to correct electrolyte abnormalities • For Grade 3-4 or complicated lower grade diarrhea consider hospitalization and IV hydration • Re-assess after 24 h 
 ○ Diarrhea resolving to baseline bowel habits or Grade \leq 1: consider restarting study treatment at reduced dose ○ Diarrhea not resolving: Start and/or continue antidiarrheal treatment (e.g., loperamide 4 mg followed by 2 mg after each episode of diarrhea [maximum: 16 mg loperamide per day]). Consider starting second line antidiarrheal or referral to gastroenterologist

Table 15. Management of Hypertension Associated with Cabozantinib

Event	Management
Subjects NOT receiving optimized anti-hypertensive therapy	
> 140 mm Hg (systolic) ^a and < 160 mm Hg OR > 90 mm Hg (diastolic) and < 110 mm Hg	
 Optimize antihypertensive medications by adding new or additional antihypertensive medications and/or increase dose of existing medications. Reduce cabozantinib treatment by one dose level if optimal antihypertensive therapy (usually to include 3 agents) does not result in BP <140 mm Hg systolic or <90 mm Hg diastolic If subject is symptomatic interrupt cabozantinib treatment

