≥ 160 mm Hg (systolic) OR ≥ 110 mm Hg (diastolic)	
 Reduce cabozantinib by one dose level^b or interrupt cabozantinib treatment per Investigator discretion. Add new or additional anti-hypertensive medications and/or increase dose of existing medications and monitor subject closely for hypotension. If optimized antihypertensive therapy (usually to include 3 agents) does not result in BP < 140 mm Hg systolic or < 90 mm Hg diastolic, cabozantinib treatment should be dose reduced further or interrupted. Cabozantinib treatment should be dose interrupted if upper limits of systolic BP (≥ 160 mm Hg) are sustained and not adequately manageable or if systolic BP is > 180 mm Hg or diastolic BP > 110 mm Hg, or if subject is symptomatic. Re-start cabozantinib treatment at the most tolerable dose and re-escalate only if BP falls to and is sustained at < 140 mm Hg systolic and < 90 mm Hg diastolic.
Hypertensive emergency ^c	
 Discontinue cabozantinib treatment.

^a Permitted dose levels are defined by individual protocols.

^b Hypertensive emergency is defined as uncontrolled elevated BP with clinical evidence of progressive or impending end-organ damage (e.g., myocardial infarction/ischemia, intracranial hemorrhage, cerebral ischemia, pulmonary edema, encephalopathy, kidney damage).

Table 16. Management of Palmar-plantar Erythrodysesthesia (PPE) associated with Cabozantinib

CTCAE v.4.0 Grade	Action To Be Taken
Grade 1	Cabozantinib treatment may be continued at the current dose if PPE is clinically insignificant and tolerable. Otherwise, Cabozantinib should be reduced to the next lower dose level ^a . Start urea 20% cream twice daily AND clobetasol 0.05% cream once daily. Reassess at least weekly; if PPE worsens at any time or does not improve after 2 weeks, proceed to the intervention guidelines for Grade 2.
Grade 2	Cabozantinib treatment may be continued if PPE is tolerated. Cabozantinib should be dose reduced or interrupted if PPE is intolerable. Continue urea 20% cream twice daily AND high potency steroid cream (e.g., clobetasol 0.05%) once daily and add analgesics (e.g., NSAIDs/gamma-aminobutyric acid agonists) for pain control if needed. Reassess at least weekly; if PPE worsens or affects self-care, proceed to the intervention guidelines for Grade 3.

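### Appendix E Table 15 omits the permanent cabozantinib stop for severe hypertension despite optimal treatment, and 7.2.3 narrows the fistula stop to an unmanageable one

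*Combined protocol and SAP*

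**What the plan says.** **Hypertension**

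- Section 7.2.3 introduces its list with "Permanently discontinue CABOZANTINIB for any of the following" and includes "hypertensive crisis or severe hypertension despite optimal medical management".
- The general stop list in 7.2.2 names "hypertensive emergency, persistent uncontrolled hypertension despite optimal medical management".
- The Hypertension paragraph in 7.2.2 says that an appendix "provides treatment guidelines for hypertension deemed related to Cabozantinib". The only stop it states itself is "Cabozantinib should be discontinued in subjects with hypertensive emergency". It cites Appendix D, which is the exosomal lipid manual; the hypertension table is Table 15 in Appendix E.
- Table 15, row for pressures above 140 and below 160 systolic, or above 90 and below 110 diastolic: "Reduce cabozantinib treatment by one dose level if optimal antihypertensive therapy (usually to include 3 agents) does not result in BP" under 140 systolic or under 90 diastolic.
- Table 15, row for 160 systolic or 110 diastolic and above: if optimized therapy fails to reach the same target, "cabozantinib treatment should be dose reduced further or interrupted". A separate bullet calls for interruption where systolic readings of 160 or more "are sustained and not adequately manageable". A re-start instruction follows. Only the hypertensive emergency row discontinues.

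**Fistula**

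- Section 7.2.2 discontinues for fistula in three places: the general stop list, the gastrointestinal paragraph and the non-gastrointestinal paragraph. None of them qualifies the fistula.
- The permanent-stop list in 7.2.3 applies to a fistula that is *unmanageable*.

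Under 6.2 (Participant Discontinuation Criteria), a toxicity that the dose-modification guidelines name as a reason for permanent discontinuation is a mandatory stop of study treatment.

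**The concern.** Staff managing raised blood pressure are sent to an appendix table. That table should end where the governing rule ends. It instead goes from pressure that cannot be managed, to interruption, to re-start, with no permanent stop short of an emergency. A site following it to the letter could return to cabozantinib a patient whom 7.2.3 takes off for good. That would be avoidable exposure in someone whose severe hypertension did not respond to optimal treatment, and also a protocol deviation.

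The fistula wording raises the same kind of risk. The protocol takes this hazard seriously: 3.2.11 excludes patients with an abdominal fistula in the preceding 6 months. A site working from the 7.2.3 list alone might still not make the stop permanent.

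**Working it through.** No formula applies to the conflict itself; the check is a comparison of texts.

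**Step 1. Set the hypertension rules side by side.**

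| Place | Emergency or crisis | Not controlled on optimal treatment, no emergency |
|---|---|---|
| 7.2.3 list | Permanent stop | Permanent stop if severe |
| 7.2.2 general list | Discontinue | Discontinue if persistent and uncontrolled |
| 7.2.2 Hypertension paragraph | Discontinue | Silent; refers to an appendix |
| Appendix E Table 15 | Discontinue | Reduce, reduce further or interrupt; then a re-start instruction |

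**Step 2. Does Table 15 cover patients who have failed optimal treatment?** Its subheading refers to subjects not on optimized therapy. Its bullets nevertheless say what to do when optimized therapy, usually three agents, does not reach target. So it does cover them.

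**Step 3. Read the re-start sentence both ways.** The sentence tells the site to resume at the best-tolerated dose and to re-escalate, with an *only if* condition that pressure has come down to, and stays, below 140 systolic and below 90 diastolic.

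- If the condition governs both actions, the drug returns only after control is regained, and a patient who never regains it stays off. The gap from 7.2.3 is then that the stop is not permanent.
- If the condition governs re-escalation alone, the drug may be resumed at a lower dose with no pressure requirement. The gap from 7.2.3 is then wider.

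The text does not settle which is meant. Neither reading supplies the permanent stop.

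**Step 4. Does the stop apply anyway?** Yes. Section 6.1 places dose modifications in Section 7, 7.2.3 names the event, and 6.2 makes a named event mandatory. The general list in 7.2.2 points the same way.

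**Step 5. Trace a manageable fistula.** Under 7.2.2 cabozantinib is discontinued, with no restart provision. That section speaks of interruption where it means a temporary hold (for example venous thrombosis and infection), so discontinuation there reads as a stop. Under 7.2.3 alone, a manageable fistula is outside the permanent list and could come under the general rule: withhold for Grade 4, or for Grade 3 or intolerable Grade 2 events that dose reduction or supportive care cannot handle. On recovery to baseline or Grade 1, a patient who was on 40 mg daily resumes at 20 mg daily. That is a route back to a drug that 7.2.2 stops.

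**Step 6. How often would Table 15 be used?** Section 7.2.2 lists hypertension among events seen in at least 20% of cabozantinib-treated subjects. If 20% held here, 0.20 × 23 = 4.6, or about 5 of the 23 planned patients, would have hypertension of some grade. This is an all-grade monotherapy figure. It suggests that the table will be used, and says nothing about how many patients would reach the disputed step.

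**The case against.** The strongest reply is that nothing is missing from the protocol as a whole. The stop is in 7.2.2 and 7.2.3, and 6.2 makes it mandatory. Table 15 can be read as the earlier steps of a ladder that 7.2.3 completes. Section 7.2.3 itself starts with withholding and resuming before it reaches the permanent list, and continued reduction under Table 5 in Section 8 ends in discontinuation. It does not define *severe* or say when optimal management has failed. For fistula, a site that follows 7.2.2 satisfies both sections.

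Much of this stands. A careful site applying the strictest text complies with all of them. But a ladder still needs its last step, and Table 15 neither states it nor refers back to 7.2.3.

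A reader might go further in three ways that the documents do not support:

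- That Table 15 leaves a patient with sustained, unmanageable systolic pressure of 160 or more on a reduced dose. Its specific bullet for that situation calls for interruption.
- That 7.2.2 requires a stop at any pressure above 140/90 on optimal treatment, because 3.2.16 defines uncontrolled hypertension that way. That is an eligibility definition, and the protocol does not carry it into the stopping rules.
- That the Hypertension paragraph independently drops the stop. It sits inside 7.2.2, whose general list contains it.

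Finally, Table 15 as readable cites a footnote c but prints only a and b, and has no counterpart block for subjects already on optimized therapy. Text may have been lost in conversion from PDF.

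**Conclusion.** The point holds as an inconsistency between safety texts that should be corrected at the next amendment. Table 15 gives a weaker hypertension rule than 7.2.2 and 7.2.3, with an ambiguous re-start condition, and 7.2.3 gives a narrower fistula rule than 7.2.2. It would be wrong to infer that the protocol has no stop for refractory severe hypertension, or that it authorizes re-treatment after a fistula: the hypertension stop is in force, and no fistula-specific restart is written anywhere.

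The size is one missing table row, one unclear sentence and one qualifying word. The documents give no rate for severe refractory hypertension or for fistula, so no count of affected patients is claimed. The conclusion assumes that the readable Table 15 is complete and that discontinuation in 7.2.2 means a lasting stop.

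**What to change.** 1. Add a permanent-discontinuation row to Table 15 for severe hypertension that persists despite optimal medical management, and a matching sentence in the 7.2.2 Hypertension paragraph. The sponsor should set the pressure threshold and keep it consistent with the 7.2.2 general stop list. The appendix reference in that paragraph can be corrected at the same time.
2. State in Table 15 that re-start after interruption requires pressure sustained below 140 systolic and below 90 diastolic.
3. Delete *unmanageable* from the 7.2.3 list, so that any diagnosed fistula is a permanent stop, in line with 7.2.2.

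If a precedence rule is wanted, it should say that the stricter stop applies. Making the 7.2.3 list prevail over other sections would let its *severe* override the possibly broader 7.2.2 wording and so weaken a safeguard.

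The cost is text edits, staff retraining and possibly a few more cabozantinib discontinuations. Sample size and the primary test do not change.

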7.2 Cabozantinib

7.2.1 Product Description and Administration

Exelixis (one of the two co-sponsors) will provide adequate supplies of Cabozantinib, which will be supplied as 40-mg yellow film-coated tablets and also as 20-mg yellow film-coated tablets.

The components of the tablets are listed below.

40 mg Cabozantinib tablets are yellow film-coated, oval shaped with no score, and debossed with "XL" on one side and "60" on the other side.

20 mg CABOMETYX tablets are yellow film-coated, round with no score, and debossed with "XL" on one side and "20" on the other side.

Table 3. Cabozantinib Tablet Components and Composition

Ingredient	Function	% w/w ^a
Cabozantinib Drug Substance (25% drug load as free base)	Active Ingredient	31.68
Microcrystalline Cellulose (Avicel® PH-102)	Filler	38.85
Lactose Anhydrous (60M)	Filler	19.42
Hydroxypropyl Cellulose (EXF)	Binder	3.00
Croscarmellose Sodium (Ac-Di-Sol®)	Disintegrant	6.00
Colloidal Silicon Dioxide	Glidant	0.30
Magnesium Stearate	Lubricant	0.75
Opadry® yellow film coating which includes HPMC 2910/hypromellose 6 cp, titanium dioxide, triacetin, and iron oxide yellow	Film Coating	4.00

^a weight fraction, expressed in percentage; HPMC, Hydroxypropyl methylcellulose

Preparation, Storage and Stability

Store at 20°C to 25°C (68°F to 77°F); excursions permitted from 15°C to 30°C (59°F to 86°F).

Administration

Refer to the treatment section for specific administration instructions. Oral: 40 mg once daily, continue as long as benefiting clinically or until unacceptable toxicity (Choueiri 2021); do not exceed 60 mg daily. Administer on an empty stomach (1 hour before or 2 hours after eating).

Note: The prescribing information (for Cometriq) describes when to give food with respect to Cabozantinib; no food should be consumed for at least 2 hours before or for at least 1 hour after the Cabozantinib dose. Swallow whole; do not crush tablets. Do not substitute Cabozantinib tablets.

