8.2 Prohibited or Restricted Medications or Therapy

Participants are prohibited from receiving the following therapies during the Screening and Treatment Phase (including retreatment for post-complete response relapse) of this trial:

- Concomitant medications that are known to prolong the QTc interval should be avoided in subjects who receive Cabozantinib until they have permanently discontinued Cabozantinib treatment (refer to <http://www.qtdrugs.org> for a list of drugs which have the potential to prolong the QTc interval).
- Anticoagulation with coumarin agents (e.g., warfarin), direct thrombin inhibitors (e.g., dabigatran), direct factor Xa inhibitor betrixaban, or platelet inhibitors (e.g., clopidogrel) are prohibited.
- Co-administration of Cabozantinib with strong inhibitors of the CYP3A4 family may increase Cabozantinib concentrations and should be avoided. See **Appendix G**.
 - Strong CYP3A4 inhibitors: if possible, avoid concomitant use with Cabozantinib. Examples of strong CYP3A4 inhibitors include: Boceprevir, clarithromycin, conivaptan, indinavir/ritonavir, itraconazole, ketoconazole, lopinavir/ritonavir, atazanavir, telaprevir, telithromycin, nefazodone, nelfinavir, posaconazole, ritonavir, saquinavir/ritonavir, and voriconazole.
 - Grapefruit, grapefruit juice, star fruit and Seville oranges may also increase plasma concentrations of Cabozantinib and should also be avoided.
 - Other drugs that inhibit CYP3A4 should be used with caution because these drugs have the potential to increase exposure (AUC) to Cabozantinib.
 - Selection of alternate concomitant medications with no or minimal CYP3A4 enzyme inhibition potential is recommended.
 - When concomitant use of strong CYP3A4 inhibitors cannot be avoided, reduce Cabozantinib dose by 20 mg.
 - Resume Cabozantinib at the dose that was used prior to initiating the strong CYP3A4 inhibitor 2 to 3 days after discontinuation of the strong inhibitor.
- Chronic co-administration of Cabozantinib with strong inducers of the CYP3A4 may significantly decrease Cabo concentrations and should be avoided. See **Appendix F**.
 - Strong CYP3A4 inducers: if possible, avoid concomitant use with Cabozantinib. Examples of strong CYP3A4 inducers include: Rifampin, phenytoin, carbamazepine, rifabutin, rifapentine, phenobarbital and St. John's wort.
 - Other drugs that induce CYP3A4 should be used with caution as these drugs have the potential to decrease exposure (AUC) to Cabozantinib.

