 - Selection of alternate concomitant medications with no or minimal CYP3A4 enzyme induction potential is recommended for subjects receiving Cabozantinib.
 - Caution must be used with discontinuing treatment with a strong CYP3A4 inducer in a subject who has been concurrently receiving a stable dose of Cabozantinib, as this could significantly increase exposure to Cabozantinib.
 - When concomitant use of strong CYP3A4 inducers cannot be avoided, increase Cabozantinib dose by 20 mg.
 - Resume Cabozantinib at the dose used prior to initiating the strong CYP3A4 inducer 2 to 3 days after discontinuation of the strong inducer.
 - Do not exceed daily dose of 60 mg (Cabozantinib).

- Antineoplastic systemic chemotherapy or biological therapy
- Immunotherapy not specified in this protocol
- Chemotherapy not specified in this protocol
- Investigational agents other than cabozantinib or pembrolizumab
- Radiation therapy: Radiation therapy to a symptomatic solitary lesion or to the brain may be allowed at the investigator's discretion.
- Live vaccines within 30 days prior to the first dose of study treatment and while participating in the study. Examples of live vaccines include, but are not limited to, the following: measles, mumps, rubella, varicella/zoster, yellow fever, rabies, BCG, and typhoid vaccine. Seasonal influenza vaccines for injection are generally killed virus vaccines and are allowed; however, intranasal influenza vaccines (e.g., FluMist®) are live attenuated vaccines and are not allowed.
- Systemic glucocorticoids for any purpose other than to modulate symptoms from an event of clinical interest of suspected immunologic etiology. The use of physiologic doses of corticosteroids may be approved after consultation with the Sponsors.

Participants who, in the assessment by the investigator, require the use of any of the aforementioned treatments for clinical management should be removed from the study. All treatments that the Investigator considers necessary for a participant's welfare may be administered at the discretion of the Investigator in keeping with the community standards of medical care.

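### The cabozantinib daily maximum is 60 mg in Sections 7.2.1 and 8.2 but 80 mg in 7.2.3, and Section 8.2 gives three unranked instructions for an unavoidable strong CYP3A4 drug

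*Combined protocol and SAP*

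**What the plan says.** **Maximum daily dose** (combined protocol and SAP)

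- Section 7.2.1, under administration: "do not exceed 60 mg daily".
- Section 7.2.3, strong CYP3A4 inducer paragraph: "The daily dose of CABOZANTINIB should not exceed 80 mg". The worked examples for the 20 mg increase there run "from 40 mg to 60 mg daily or from 20 mg to 40 mg daily". The same section's reduction steps include "If previously receiving 60 mg daily dose, resume treatment at 40 mg daily".
- Section 8.2, strong CYP3A4 inducer bullets: "Do not exceed daily dose of 60 mg (Cabozantinib".
- Section 8, Table 5: level 0 is 40 mg daily, level -1 is 20 mg daily, level -2 is 20 mg every other day, and level -3 stops cabozantinib.

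**Strong CYP3A4 drugs**

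Section 8.2 puts strong inhibitors and inducers in its list of prohibited therapies and asks that they be avoided if possible. For inhibitors it then says "When concomitant use of strong CYP3A4 inhibitors cannot be avoided, reduce Cabozantinib dose by 20 mg", and it gives the matching 20 mg increase for inducers. The paragraph that closes the list says that participants who "require the use of any of the aforementioned treatments for clinical management should be removed from the study". The next paragraph says that a need for a prohibited medication may require stopping study therapy, and that continuing requires the agreement of investigator, sponsor and participant.

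**Tablets**

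Section 7.2.1 states that 40 mg and 20 mg tablets are supplied. It describes the 20 mg tablet as marked 20 and the 40 mg tablet as marked 60.

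**The concern.** A dose limit protects patients only if it has one value. Here two sections give one figure and a third gives another. Sections 7.2.3 and 8.2 address the same strong-inducer adjustment, so the two figures cannot be read as limits for different settings.

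The instructions on CYP3A4 drugs are more likely to be needed in practice. The Section 8.2 list of strong inhibitors includes common anti-infectives, and Section 7.2.2 notes that infections are common in cancer patients. A site with such a patient can find support in Section 8.2 for adjusting the dose, for removing the patient, or for seeking agreement to continue. Two sites, or one site on two occasions, could act differently and each claim compliance.

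For the analysis, the question is what removal means. If it means leaving the study, progression follow-up may stop, and the primary endpoint would be censored at a time set by a concomitant medication.

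**Working it through.** There is no sample-size or power figure to reproduce. The check sets the passages side by side and applies the protocol's own 20 mg rule to its own dose levels.

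**1. Where the two limits differ in effect**

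- Level -1 plus one inducer step: 20 + 20 = 40 mg. Within both limits.
- Level 0 plus one inducer step: 40 + 20 = 60 mg. Equal to the limit in 7.2.1 and 8.2, and below the limit in 7.2.3.
- From 60 mg, one further step: 60 + 20 = 80 mg. At the limit in 7.2.3, and 20 mg above the limit in 7.2.1 and 8.2 (80/60 = 1.33).

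Table 5 starts at 40 mg and only goes down, so a single step from any Table 5 level stays at or below 60 mg. The conflict bites only for a patient already above 40 mg. Section 7.2.3 contemplates that state, because it lists 60 mg as a possible prior dose.

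**2. Adjust, remove or continue**

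- Adjust: Section 8.2, inhibitor and inducer bullets, and Section 7.2.3.
- Remove from the study: Section 8.2, closing paragraph of the list, covering every treatment named above it.
- Continue by agreement: Section 8.2, following paragraph.

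No sentence exempts the CYP3A4 bullets from the removal sentence, and none ranks the three.

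**3. What removal means for PFS**

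Section 6.2 says that stopping study intervention is not withdrawal from the study and that follow-up continues. It says that a participant who withdraws is no longer followed at scheduled visits. Section 8.2 speaks of removal from the study, not from treatment, and does not point to either rule. Sections 9.4 and 9.7.2 keep patients who received study drug in the primary analysis, so a removed patient is not deleted but could be censored early. Section 9 gives no censoring rule for this case.

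**4. The 20 mg reduction at the reduced levels**

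- Level -1: 20 − 20 = 0 mg.
- Level -2, on a dosing day: 20 − 20 = 0 mg.

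This concerns only a patient who is at 20 mg and also needs a strong inhibitor. Neither 7.2.3 nor 8.2 says what a result of zero means in terms of Table 5.

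**5. Tablet marking**

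The 20 mg description matches its strength (20 and 20). The 40 mg description does not (40 and 60). The actual imprint is not in the documents.

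**The case against.** The strongest reply is that little turns on the two limits. One inducer step from any Table 5 level cannot pass 60 mg, and the examples in 7.2.3 stop there. That stands, and it limits the practical reach of the conflict. It does not remove it, because the same section lists 60 mg as a prior dose.

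A second reply is that the CYP3A4 bullets are a specific exception within a general list, softened by the agreement route. That is a reasonable reading, but the text does not say so. The removal sentence covers all the treatments listed, and the agreement route adds a third instruction without ranking the other two.

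A reader might also infer several stronger points that the documents do not support:

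- **That 7.2.3 authorises 80 mg.** It states a ceiling. The only increase it describes is a single 20 mg step, and a ceiling does not authorise a second one.
- **That two removals would use up the 23 − 21 = 2 patients allowed for in Section 9.2.** Treated patients stay in the PFS analysis, no passage makes a removed patient unevaluable, and no frequency of strong CYP3A4 drug use is given.
- **That level -2 gives a negative dose.** This comes from averaging alternate-day dosing to 10 mg a day before subtracting. On a dosing day the result is zero.
- **That a patient raised to 60 mg has no way down because Table 5 starts at 40 mg.** Section 7.2.3 gives the step from 60 to 40 mg.
- **That the imprint text would lead to the wrong strength being given.** Only 40 mg and 20 mg tablets are said to be supplied.

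**Conclusion.** The contradictions are real and stand in the current protocol text. The daily maximum has two values, 20 mg apart, for the same inducer adjustment; the difference takes effect only for a patient already above 40 mg. Section 8.2 gives three instructions for an unavoidable strong CYP3A4 drug without saying which governs, and this can arise at any dose level.

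The effect on the primary endpoint is possible early censoring, not loss from the analysis set. Its size cannot be estimated, because the documents do not say how often such drugs are expected. It also depends on removal being read as study withdrawal; if follow-up continues as in Section 6.2, the effect on PFS follow-up disappears. The undefined reduction at 20 mg and the tablet marking are smaller points of the same kind.

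The text should be corrected because it bears on patient safety and on who remains on treatment and in follow-up. Nothing here shows that the sample size or the test is wrong, and no view is taken on which limit or rule is right.

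**What to change.** In the next amendment:

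1. Reconcile Sections 7.2.1, 7.2.3 and 8.2 to a single maximum daily dose.
2. Reconcile the adjust, remove and continue instructions in Section 8.2 so that it is clear which one governs for strong CYP3A4 drugs.
3. State whether removal in Section 8.2 means stopping treatment with follow-up continuing as in Section 6.2, or withdrawal from the study. State in Section 9.4 how PFS is handled in that case.
4. Reconcile the 20 mg adjustment in Sections 7.2.3 and 8.2 with the Table 5 levels, including the two levels that use 20 mg.
5. Check the 40 mg tablet description in Section 7.2.1 against the supplied product.

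The sponsor, investigator and manufacturer decide the values and the rules. The cost is text edits and a pharmacy check, with no added patients or procedures.
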